Key Eligibility Criteria:	The eligibility criteria for this study are consistent with previous depatuxizumab mafodotin clinical studies where eye toxicities are the most common treatment-related adverse events observed, and these toxicities define the DLT for depatuxizumab mafodotin. Subjects have histologically confirmed newly diagnosed grade IV glioblastoma or gliosarcoma, supratentorial in location, with EGFR amplification.
Study Drug and Duration of Treatment:	Subjects will receive depatuxizumab mafodotin 2.0 mg/kg during the chemoradiation phase (consisting of radiation and temozolomide [RT/TMZ]) and depatuxizumab mafodotin 1.25 mg/kg during adjuvant therapy with TMZ. Subjects will be randomized to one of 3 prophylactic ophthalmologic treatments (SS, SS/VC, or ES/VC). Depatuxizumab mafodotin will be administered every 2 weeks during standard 6-week RT/TMZ therapy, followed by a 4-week recovery period. During adjuvant therapy, depatuxizumab mafodotin will be administered every 2 weeks for 12 cycles (28 days/cycle).
Date of Protocol Synopsis:	28 May 2019

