2 INTRODUCTION

2.1 Background and Rationale

Why Is This Study Being Conducted

Glioblastoma (GBM) is the most common and most aggressive type of primary brain tumor in adults, affecting 8,000 to 10,000 people per year in North America alone.¹ The current standard-of-care therapy for newly diagnosed glioblastoma following surgical debulking is radiation therapy (RT) in combination with temozolomide (TMZ), followed by 6 months of further TMZ monotherapy.² Despite this multimodal approach, median survival is 1 – 2 years. There is an urgent need to develop novel therapeutics that can improve outcome in glioblastoma patients.

A substantial proportion of GBM tumors are characterized by Epidermal Growth Factor Receptor (EGFR) overexpression and amplification. When present, EGFR amplification has been shown to be maintained throughout the natural history of the disease. These features make EGFR a target for therapeutic intervention. Depatuxizumab mafodotin (formerly known as ABT-414) is an antibody-drug conjugate (ADC) that incorporates the ABT-806 antibody, which is covalently bound to an auristatin microtubule-disrupting toxin (mono methyl auristatin form [MMAF]) via a non-cleavable maleimido-caproyl (mc) linker. Depatuxizumab mafodotin is currently being investigated in late phase clinical trials of patients with newly diagnosed glioblastoma with amplified EGFR. The dose-limiting toxicities (DLTs) observed after depatuxizumab mafodotin exposure have been limited to ocular side effects (OSEs) with symptoms that manifest as a result of formation of corneal epithelial microcysts, a syndrome referred to as microcystic keratopathy. It is hypothesized that depatuxizumab mafodotin is taken up into rapidly dividing cells of the corneal epithelium, mainly by non-selective, EGFR-unrelated mechanism; toxin is then released inside the cell, causing damage predominantly to the transient amplifying cells located within the basal cell layer, with relative sparing of the more slowly dividing corneal stem cells in the limbus. This damage results in cellular death leading to the formation of epithelial microcysts. The epithelial microcysts then travel towards the central cornea and are sloughed off as part of normal cornea regeneration. Therefore, as the cornea regenerates, the symptoms resolve and the effects of depatuxizumab mafodotin should be transient after treatment discontinuation.

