3.5 Ophthalmology Exam

Qualified medical personnel will perform the ophthalmologic examination as outlined in Section 2.1, Section 2.2, and Appendix C. Additional exams may be performed as clinically indicated.

Ophthalmology exams are to be performed 7 to 14 days after the 2nd and 3rd infusions of Depatux-M and must be completed prior to the next infusion of Depatux-M. Exams will at a minimum include assessment of visual acuity (as described below, using LogMAR scale and Appendix D), intraocular pressure, and slit lamp examination, as well as assessment for symptoms of eye pain and photophobia, and results will be recorded in the corresponding CRF (Appendix C).

Visual Acuity (VA) and Best corrected visual acuity (BCVA)

Instructions for obtaining visual acuity assessments at each ophthalmology visit (including the visual correction to be used for VA assessments, when BCL should be in place during VA assessment, and when manifest refraction is to be performed to assess BCVA) are described below. Visual acuity will be measured using the LogMAR scale in all cases. Visual acuity will be captured with baseline glasses (VAcc) or without glasses (VAsc) if the subject does not require correction at baseline during all ophthalmology visits. Best Corrected Visual Acuity (BCVA) will be assessed with manifest refraction during specified visits outlined in the protocol.

Baseline Ophthalmic Examination

- VA with baseline correction (cc or sc) *without BCL* – OD, OS, OU
 - Record glasses prescription if applicable
 - Record without glasses if subject does not require correction at baseline
 - *The same prescription will be used to measure VA (cc or sc) for all post-baseline visits*
- BCVA (with manifest refraction) – OD, OS, OU will be recorded

Post-baseline visits (prior to BCL intervention)

- VA with baseline correction (cc or sc) *without BCL* – OD, OS, OU
- *If VA OU (cc or sc) has declined ≥ 0.3 LogMAR from baseline OR if CEAE Grade ≥ 3 , place BCL and obtain the following:*
 - VA with baseline correction (cc or sc) *with BCL* – OD, OS, OU
 - BCVA (manifest refraction) *with BCL* – OD, OS, OU

Post-baseline visits (if BCLs are being used)

- VA with baseline correction (cc or sc) *without BCL* – OD, OS, OU – omit if BCL is not changed at the visit
- VA with baseline correction (cc or sc) *with BCL* – OD, OS, OU
- *If VA OU (cc or sc) with BCL decline ≥ 0.3 LogMAR from baseline remains, obtain the following:*

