5.0 Study Objectives, Design and Procedures

5.1 Objectives

Primary objective

Estimate the percentage of subjects in each prophylactic treatment arm who require a change in ocular side effect (OSE) management due to inadequate control of OSEs.

Secondary objectives

Assess the effects of intervention with bandage contact lenses (BCL) on visual acuity for subjects who require intervention due to inadequate control of OSEs.

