5.3 Endpoints

5.3.1 Primary Endpoint

The primary endpoint is defined as the percentage of subjects with either a ≥ 3 -line decline from baseline ($\geq +0.3$ on LogMAR scale) (Bailey IL, Lovie-Kitchin, 2013) in

visual acuity (with baseline correction determined at the screening ophthalmology visit) or \geq Grade 3 OSE severity on the Corneal Epithelial Adverse Event (CEAE) scale, either of which will indicate inadequate control of OSEs requiring a change in OSE management strategy. The primary endpoint is assessed over 8 weeks after initiation of depatuxizumab mafodotin treatment regardless of phases.

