11.2 Analysis of Primary Endpoint

The proportion of patients who met the primary endpoint defined as (a) either $\geq +0.3$ change on LogMAR scale in baseline adjusted visual acuity or (b) incidence of \geq Grade 3 Corneal Epithelial Adverse Event (CEAE, CMQ: 80000184), anytime over 8 weeks after initiation of Depatux-M and prior to BCL intervention will be summarized by treatment arms and in overall population. This analysis will also be repeated for the Post-BCL intervention period. For the Post-BCL intervention period, analysis will be

limited to the patients who received BCL intervention and baseline will be re-set to the last assessment prior to start of BCL intervention.

Time to the first occurrence (onset) of any CEAE will be assessed using Kaplan Meier methodology and median time to first onset of any corneal AE (along with 95% CI). This analysis will be repeated for Grade 3 or higher corneal AEs.

Time to onset will be measured in days relative to the date of first dose date to the start date of the first occurrence of CEAE. If a subject has not experienced an CEAE, the subject will be censored on the subject's last assessment date (i.e., the day of the subject's last known laboratory assessment, last known vital sign assessment, last known physical exam, last known ocular exam, last known tumor assessment, or last known follow-up visit, whichever is the latest) or 49 days from the subject's last treatment (Depatux-M), whichever is earliest. If the subject has no post-baseline assessment, the data will be censored on the day of first dosing date.

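### The only planned outcome analysis after bandage-lens fitting has no comparator, no window end and a moving baseline, so it cannot answer the SAP's retained objective on the lens and visual acuity

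*SAP*

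**What the plan says.** SAP 5.1 keeps the objective: "Assess the effects of intervention with bandage contact lenses (BCL) on visual acuity", in subjects who need intervention. Protocol 3.3 had matched it with endpoints for BCL effectiveness, among them LogMAR change across the intervention and recovery to less than a 3-line loss. It also asked for assessment by phase, where appropriate, because the doses differ. SAP 5.3.2 and 11.3 carry none of those endpoints. The acuity and time-to-event summaries in 11.3 stop at BCL start.

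The main analysis in SAP 11.2 counts subjects with an acuity loss of at least +0.3 LogMAR or a Grade 3 or higher corneal epithelial adverse event (CEAE), "anytime over 8 weeks after initiation of Depatux-M and prior to BCL intervention". SAP 5.3.1 describes that endpoint as "assessed over 8 weeks after initiation of depatuxizumab mafodotin treatment regardless of phases". Section 11.2 then adds: "This analysis will also be repeated for the Post-BCL intervention period". The repeat is "limited to the patients who received BCL intervention and baseline will be re-set to the last assessment prior to start of BCL intervention". No end of the post-BCL period is given, and nothing says whether acuity with or without the lens is used. SAP 7.2 takes the worst value when several fall on one day.

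On schedule, the Protocol Synopsis has drug given "every 2 weeks during standard 6-week RT/TMZ therapy, followed by a 4-week recovery period". On biology, Protocol 2.1 expects that "as the cornea regenerates, the symptoms resolve and the effects of depatuxizumab mafodotin should be transient after treatment discontinuation". Operations Manual 3.5 says that when a subject meets the trigger, sites should "place BCL and obtain the following", namely acuity with the lens. This follows the acuity without the lens already taken at that visit.

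**The concern.** The trigger for a lens tends to be met after the second or third infusion, just before drug exposure is due to stop for several weeks and then resume at a lower dose. The repeat follows only lens recipients through that change and compares them with nobody. If few have an event after fitting, the figure will be set beside the BCL objective, yet it cannot tell lens benefit from time off drug or reduced exposure. At stake is the one secondary objective about the intervention. The prophylaxis arms and the primary estimate before BCL are not affected.

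**Working it through.** The plan gives no figure for this analysis. Protocol Table 6 concerns the primary endpoint. Its intervals are Wald intervals and reproduce: for 8/30, 26.7% ± 1.96·√(0.267·0.733/30) = 26.7% ± 15.8, or 10.8 to 42.5. The check here is a day count of the planned schedule.

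**Inputs.** Infusions of 2.0 mg/kg fall on Days 1, 15 and 29 (Protocol 4.1). Radiation takes about 6 weeks, at most 7. The adjuvant phase starts about 28 days after chemoradiation ends, at 1.25 mg/kg every 2 weeks for 12 cycles. Eye exams are due 7 to 14 days after infusions 2 and 3 (Operations Manual 3.5), so about Days 22-29 and 36-43. Operations Manual 2.1 also lists an exam at Week 3 Day 1. Week 9 Day 1 (Day 57) is a telephone CEAE only.

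**Gap.** Radiation ending on Day 40-42 puts the first adjuvant dose on Day 68-70, and 68 − 29 = 39 to 70 − 29 = 41 days. Counting Cycle 1 Day 1 as Day 71 gives 42. With 7 weeks of radiation, 49 + 28 − 29 = 48.

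**Dose.** (2.0 − 1.25)/2.0 = 37.5% lower, or 1.0 mg/kg/week before the gap and 0.625 after it.

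**Reading 1: the 8-week limit carries over (to Day 56).** There are no adjuvant days. Days 30-56 number 27. On a stricter count, where each infusion covers 14 days, the gap starts on Day 43 and supplies up to 14 days.

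| Fitted on | Days left | Infusions on or after fitting | Gap share from Day 30 | Gap share from Day 43 |
|---|---|---|---|---|
| Day 15 | 41 | 2 | 27/41 = 66% | 14/41 = 34% |
| Day 22 | 34 | 1 | 27/34 = 79% | 14/34 = 41% |
| Day 29 | 27 | 1 (same day) | 100% | 14/27 = 52% |
| Day 36 | 20 | 0 | 100% | 14/20 = 70% |
| Day 43 | 13 | 0 | 100% | 100% |

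A subject fitted at Week 7 has no infusion and no scheduled eye exam left in the window.

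**Reading 2: 56 days from fitting, first adjuvant dose on Day 70.** Mean dose rate, total mg/kg over 8 weeks:
- Day 15: (2.0 + 2.0 + 1.25)/8 = 0.66
- Day 22: (2.0 + 1.25)/8 = 0.41
- Day 29: (2.0 + 2 × 1.25)/8 = 0.56
- Day 36: (2 × 1.25)/8 = 0.31
- Day 43: (3 × 1.25)/8 = 0.47

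All are below the 1.0 mg/kg/week that preceded the lens.

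**Reading 3: open to last dose + 49 days.** The last planned infusion is 70 + 23 × 14 = Day 392, so follow-up ends on Day 441. Adjuvant days number 441 − 69 = 372. The share is 372/426 = 87% for a Day 15 fitting and 372/398 = 93% for Day 43. These are planned calendar days; Protocol Appendix E ends sponsor collection of targeted eye-exam data for continuing subjects, so late acuity will be sparser.

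**Reset baseline.** A subject fitted at exactly +0.3 must reach 0.3 + 0.3 = +0.6 from study baseline to count as a new acuity event. Unchanged loss scores as no event.

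**Numbers.** Recipients are not reported. Assuming 26.7% (lowest row of Table 6) to 61% (Grade 3 or higher corneal rate in the parallel Phase 3 trial, Protocol 2.2) of the 40 enrolled, 0.267 × 40 ≈ 11 to 0.61 × 40 ≈ 24 subjects enter, about 4 to 8 per arm.

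**The case against.** The SAP is abbreviated and descriptive, tests nothing about BCL and makes no claim for it. An uncontrolled before-after comparison was the protocol's own design, and no SAP edit can supply a control. That stands. It limits the harm to interpretation, but the objective is still listed and this is the only result that can be set against it.

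Several stronger readings are tempting and are not supported:
- *The post-BCL period is mainly off drug.* This depends on the undefined window. With the 8-week limit and the stricter count it fails for fittings on Days 15-22 (34-41%). If open-ended, most time is on drug at lower exposure, which is not recovery.
- *Few events are to be expected even if the lens does nothing.* No corneal recovery time is given, and Protocol 2.1 speaks of stopping treatment, not of a planned pause. A longer window with renewed dosing adds chances for events, and an ongoing Grade 3 or higher CEAE may still count.
- *Fitting selects subjects at their worst.* The lens is placed when a threshold is met, which need not be the peak; subjects fitted at Week 3 or 5 still face 2.0 mg/kg infusions.
- *The same-visit pair is free of confounding.* It is open-label and sequential, and it shows only the immediate effect.

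The gap length is also not fixed. Operations Manual 5.1 lets infusions move as late as the last radiation day, which would shorten the gap to about 28 days. Extra exams are allowed when clinically indicated.

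**Conclusion.** The concern holds for lenses fitted in the chemoradiation phase, most clearly at Week 5 or Week 7. Under the 8-week limit, 52-100% of the time after those fittings is infusion-free gap on the stricter count, and all of it on the plain count. If the period is open-ended, about 90% or more is adjuvant time at 62.5% of the earlier dose rate. In either case a low post-BCL proportion cannot be attributed to the lens.

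The reset baseline adds to this on the acuity side, while an ongoing severe CEAE may pull the other way. Neither the net direction nor the size of the bias can be computed, because fitting dates and recovery time are not in the documents. Lenses first fitted in the adjuvant phase face neither the gap nor the planned step-down; for them the missing comparator, undefined window and reset baseline remain. The day counts assume the planned schedule with radiation ending on Day 42. This merits a change to the SAP but does not touch the primary estimate.

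**What to change.** 1. **SAP 11.3.** Add, as the acuity measure of BCL effect, the within-subject difference at the fitting visit in both-eyes acuity with baseline correction: LogMAR without the lens minus LogMAR with it, so that positive values favour the lens. Operations Manual 3.5 and its Appendix C already collect both. Report the number of pairs, the mean and a 95% CI. Among subjects at +0.3 or worse from study baseline without the lens, report the percentage below +0.3 with it; subjects fitted for CEAE grade alone are outside that denominator.
2. **SAP 7.2.** Exempt with-lens and without-lens acuity from the worst-same-day rule, which would otherwise collapse the pair.
3. **SAP 11.2, post-BCL repeat.** Define the window. State that with-lens acuity is used. Measure acuity change from study baseline as well as from the reset one. Report by treatment phase at fitting and by whether an infusion was given between fitting and the assessment. State that the proportion is not attributable to BCL.

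The cost is SAP wording and one small table from data already collected, with no change to visits or treatment. The downsides are small row counts and a paired contrast that says nothing about durability or symptom relief.

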11.3 Analysis of Secondary Endpoints

The maximum change from baseline in visual acuity on baseline corrected LogMAR scale prior to BCL intervention will be summarized by treatment arms and in overall population.

Kaplan-Meier plot for Time to BCL intervention will be produced. Time to BCL is defined as time from the randomization to the start date of BCL (as recorded in "Study Drug Administration - Bandage contact lens" CRF page). For subjects did not use BCL will be right-censored on the last assessment date.

In addition, Time to either $\geq +0.3$ change on LogMAR scale in baseline adjusted visual acuity or grade 3 or higher CEAE prior to BCL intervention will also be analyzed. For this analysis, $+0.3$ change on LogMAR scale in baseline adjusted visual acuity before the start date of BCL or grade 3 or higher CEAE prior to the start date of BCL intervention will be considered as events. If a patient receives BCL intervention without experiencing any one of these two events will also be considered as event on the start date of BCL

intervention. If a patient neither receives BCL intervention nor experiences any one of these two events, his/her time will be right-censored on the last assessment date.

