3.3 Secondary Endpoints

Secondary endpoints will be assessed as below over 8 weeks after initiation of depatuxizumab mafodotin treatment, assessed separately for the chemoradiation phase and adjuvant phase, as appropriate, as different doses of depatuxizumab mafodotin are used in each phase. The effectiveness of the initial prophylactic strategy and of the BCL-intervention will be assessed separately, as will be resolution of OSEs after interruption/discontinuation of depatuxizumab mafodotin.

Effectiveness of Prophylactic Regimen	Effectiveness of BCL Intervention

 • Maximum change from baseline on LogMAR scale • Time to BCL intervention • Dose interruptions due to OSEs (% subjects) • Dose reductions due to OSEs (% subjects) • Cumulative dose of depatuxizumab mafodotin received (mg/kg) (during chemoradiation and during adjuvant treatment) • CEAE grade, at each visit 	
 • Change in LogMAR (pre- to post-intervention, then followed longitudinally) • Recovery to < 3-line decline from baseline (< +0.3 LogMAR) in visual acuity (% subjects) • Dose interruptions due to OSEs (% subjects) • Dose reductions due to OSEs (% subjects) • Time to restart depatuxizumab mafodotin (if interrupted) • CEAE grade, at each visit, post BCL intervention
Resolution of OSEs	

 • Time to OSE symptom resolution after drug discontinuation (reversibility) • Time to re-initiation of depatuxizumab mafodotin after dose interruption 	

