Effectiveness of the prophylactic strategies will be assessed during the first 8 weeks of each phase of treatment (Chemoradiation Phase and Adjuvant Phase). Subjects who discontinue depatuxizumab mafodotin for any reason will receive regular follow-up for assessment of AEs and ophthalmologic examinations until resolution of OSEs to evaluate the reversibility of depatuxizumab mafodotin-related OSEs.

Figure 1. Study Design

Abbreviations: GBM = glioblastoma; RT = radiation therapy; TMZ = temozolomide

Figure 2. Depatuxizumab Mafodotin Intervention Strategy for Inadequate Control of Ocular Side Effects

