- Cold compress: Starting 5 minutes prior to start of infusion and continuing for 30 minutes past end of infusion; then at least 2 hours total/day during remainder of infusion day and for 2 days after infusion. The cold compress should be applied in increments no longer than 30 min (could be shorter if the patient is uncomfortable).

With the exception of care measures described below as allowed at any time, other prophylactic or supportive measures are not allowed during the initial prophylaxis phase, unless prior approval is obtained from the AbbVie Medical Monitor.

Bandage Contact Lens (BCL) Intervention

If any subject in Arm A, Arm B, or Arm C has a ≥ 3 -line loss in visual acuity ($\geq +0.3$ change from baseline by LogMAR) OR a CEAE \geq Grade 3 ocular side effect, the subject will then receive BCL intervention in addition to the assigned initial prophylactic regimen.

With the exception of care measures described below as allowed at any time, additional measures besides BCL and the original prophylactic regimen are prohibited during the BCL intervention phase, unless prior approval is obtained from the AbbVie Medical Monitor.

Investigator Discretion

Subjects who have a \geq Grade 3 CEAE event despite/after addition of BCL intervention to the initial prophylactic regimen will enter the Investigator Discretion phase, at which point there will be no restrictions on prophylactic or supportive measures used for OSE management.

Subjects who complete 8 weeks of adjuvant therapy (8 weeks after the first adjuvant dose of depatuxizumab mafodotin) will be allowed to enter in the Investigator Discretion phase regardless of CEAE Grade, visual acuity or BCL intervention.

Supportive Care Measures Allowed at Any Time

The following supportive care measures are allowed at any time, regardless of the current phase of OSE management:

- Lubricant Eye Drops
- Artificial Tears
- Antibiotics
- Sunglasses

Information on other allowable medications (prior to eligibility for the Investigator Discretion phase) may be described in the Operations Manual.

Please reference Section 5 "Study Drug" of the Operations Manual for more information on treatments administered in this study.

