TREATMENT	
 Radiation and TMZ Depatuxizumab mafodotin 	
 Prophylactic regimen* (Arm A = SS treatment, Arm B = SS/VC, or Arm C = ES/VC)

Abbreviations: ES = enhanced steroids; SS = standard steroids; TMZ = temozolomide; VC = vasoconstrictors and cold compress

* Prophylactic regimen details are outlined in Section 5.1.

Chemoradiation Phase: Week 3 Day 1 and Week 5 Day 1

INTERVIEW	
 Adverse event assessment Prior/concomitant therapy 	
 Corneal Epithelial Adverse Event assessment
PRO	
 Visual Quality of Life (vQOL) Visual Symptoms Questionnaire 	
EXAM	
 Ophthalmology exam Weight 	
 Vital signs Physical exam if clinically indicated
CENTRAL LAB	
 Chemistry 	
 Hematology
TREATMENT	
 Prophylactic regimen* (Arm A = SS treatment, Arm B = SS/VC, or Arm C = ES/VC) 	
 Radiation and TMZ Depatuxizumab mafodotin

Abbreviations: ES = enhanced steroids; SS = standard steroids; TMZ = temozolomide; VC = vasoconstrictors and cold compress

* Prophylactic treatment details are outlined in Section 5.1.

Chemoradiation Phase: Week 7 Day 1

INTERVIEW	
 Adverse event assessment 	
 Corneal Epithelial Adverse Event assessment
PRO	
 Visual Quality of Life (vQOL) Visual Symptoms Questionnaire 	
EXAM	
 Ophthalmology exam 	
CENTRAL LAB	
 Chemistry 	
 Hematology

Chemoradiation Phase: Week 9 Day 1

INTERVIEW	
 Corneal Epithelial adverse event assessment (by phone) 	
-----------	--	--

Adjuvant Phase: Cycle 1 Day 1, Cycle 1 Day 15, Cycle 2 Day 1 and Cycle 2 Day 15:

INTERVIEW	
 Adverse event assessment 	
 Prior/concomitant therapy Corneal Epithelial Adverse Event assessment
PRO	
 Visual Quality of Life (vQOL) (Cycle 1 Day 1 only) 	
 Visual Symptoms Questionnaire (Cycle 1 Day 1 only)

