5.3.2 Secondary Endpoints

Following secondary endpoints will be assessed:

- Maximum change from baseline on LogMAR scale
- Time to BCL intervention
- Cumulative dose of depatuxizumab mafodotin received (mg/kg) (during chemoradiation and during adjuvant treatment)

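### SAP 11.3 drops the protocol's 8-week window for maximum LogMAR change, so the maximum is taken over unequal, outcome-dependent numbers of exams before bandage contact lens use

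*SAP*

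**What the plan says.** **The endpoint in the SAP.** Section 5.3.2 lists "Maximum change from baseline on LogMAR scale" with no time window. Section 11.3 gives the analysis: "The maximum change from baseline in visual acuity on baseline corrected LogMAR scale prior to BCL intervention will be summarized by treatment arms", and for the overall population. The only limit is the start of BCL.

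**The endpoint in the protocol.** Section 3.3 states: "Secondary endpoints will be assessed as below over 8 weeks after initiation of depatuxizumab mafodotin treatment", with the chemoradiation and adjuvant phases taken separately where appropriate because the doses differ. Section 4.1 states: "Effectiveness of the prophylactic strategies will be assessed during the first 8 weeks of each phase of treatment", and names both phases.

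**The primary endpoint in the SAP.** Section 11.2 carries both limits: "anytime over 8 weeks after initiation of Depatux-M and prior to BCL intervention".

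**What starts BCL.** Under Protocol 5.7, on a LogMAR worsening of 0.3 or more or a corneal epithelial adverse event (CEAE) of Grade 3 or higher, "the subject will then receive BCL intervention in addition to the assigned initial prophylactic regimen".

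**What else can change late in the study.** Protocol 4.1 and 5.7 let subjects who finish 8 adjuvant weeks move to Investigator Discretion management whether or not they have used BCL.

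**State of the trial.** SAP 4.0 records 40 subjects enrolled, most without long follow-up. Under Protocol Appendix E the sponsor does not collect targeted eye-exam data for subjects who continue treatment.

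**The concern.** Section 11.2 states the 8 weeks and the BCL limit as two separate conditions. Section 11.3 states only the second, so no general SAP convention supplies the first. A programmer following 11.3 as written would take each subject's worst reading over all exams up to BCL, however late.

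Two features make this more than an omission of wording. A maximum over repeated noisy readings rises with the number of readings. And the period ends at an event caused partly by the outcome being measured. A regimen that postpones BCL therefore gives its subjects more exams, and more chances of a high reading, than one that fails early. The comparison of arms on visual acuity is then no longer over a common period, and the usual direction of the error is against the better regimen.

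There is also a question of meaning. A reading taken before BCL but after 8 adjuvant weeks may come from a subject already on unrestricted eye care, so it need not reflect the assigned prophylaxis.

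**Working it through.** **1. The plan's own figures.** The documents give no precision or effect figure for maximum LogMAR change. Protocol Table 6 is for the primary endpoint only. It reproduces as a Wald interval: 8/30 = 26.7%, ± 1.96 × √(0.267 × 0.733 / 30) = ± 15.8 points, giving 10.8 to 42.5. It does not bear on this point.

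**2. Exams in each window** (Operations Manual 2.1).
- Chemoradiation: Weeks 3, 5 and 7, so 3 post-baseline exams. Week 9 is a telephone CEAE assessment without an eye exam.
- Adjuvant Cycles 1 and 2: one exam at each of 4 visits.
- Adjuvant Cycles 3 to 12: every 4 weeks, about 10 exams.

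The first 8 weeks hold 3 exams. The open wording allows 3 + 4 + 10 = 17 through Cycle 12. Post-treatment exams would add to that.

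**3. Growth of a maximum from noise alone.** For k independent normal readings the expected maximum is 0.85 SD (k = 3), 1.35 SD (k = 7) and 1.79 SD (k = 17). With an assumed within-subject SD of 0.07 to 0.10 LogMAR:
- 3 exams: 0.85 × 0.07 to 0.85 × 0.10, about 0.06 to 0.08.
- 17 exams: 1.79 × 0.07 to 1.79 × 0.10, about 0.13 to 0.18.

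**4. Effect on the arm contrast.** The documents give no LogMAR SD, arm effect or trigger rate, so all of these are assumptions:
- control mean worsening 0.10, 0.15 or 0.20, with the better arm at 50% or 80% of it;
- three time courses;
- between- and within-subject SDs of 0.10 and 0.07, or 0.15 and 0.10;
- BCL starts for CEAE grade alone at five pairs of per-exam rates;
- complete follow-up, or stopping at a mean of about 20 weeks.

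That makes 3 × 2 × 3 × 2 × 5 × 2 = 360 scenarios, with 40,000 simulated subjects per arm. Observation stops at the first exam with +0.3 or a CEAE trigger. The contrast is control minus better arm, averaged over 72 scenarios per row. Over 8 weeks without any BCL cut it is 0.044 in every row. A reversal means the better arm looks worse by more than 0.002.

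| CEAE-only trigger per exam, control / better | Open window | 8-week window | Mean exams, open | Mean exams, 8-week | Reversals, open | Reversals, 8-week |
|---|---|---|---|---|---|---|
| 0% / 0% | 0.040 | 0.042 | 8.1 / 9.4 | 2.6 / 2.7 | 0 of 72 | 0 of 72 |
| 5% / 5% | 0.040 | 0.041 | 6.1 / 7.0 | 2.5 / 2.6 | 0 of 72 | 0 of 72 |
| 10% / 5% | 0.023 | 0.036 | 4.8 / 7.0 | 2.4 / 2.6 | 10 of 72 | 0 of 72 |
| 20% / 5% | −0.003 | 0.024 | 3.4 / 7.0 | 2.2 / 2.6 | 39 of 72 | 8 of 72 |
| 30% / 5% | −0.022 | 0.014 | 2.6 / 7.0 | 2.0 / 2.6 | 52 of 72 | 26 of 72 |

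The open contrast was smaller than the 8-week contrast by more than 0.002 in 284 of 360 scenarios, but in only 70 of the 144 with equal trigger rates. Of the 101 reversals under the open window, 67 came with complete follow-up and 34 with truncated follow-up. These counts describe the chosen grid and are not probabilities.

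**5. Precision at the actual size.** 40 / 3 is about 13 per arm. With the simulated SD of about 0.135, the SE of an arm difference is 0.135 × √(2/13) = 0.053. The average shifts between open and 8-week windows are 0.001 to 0.036 (for example 0.036 − 0.023 = 0.013 at 10% / 5%), all below one SE.

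**The case against.** A reader might infer that the open window in general hides or reverses a prophylaxis benefit, or that the endpoint rewards early failure. The documents do not support that. Operations Manual 3.5 measures visual acuity without the lens and then places it, so a subject sent to BCL by visual acuity already carries a maximum of at least +0.3. A subject still without BCL under the trigger rule has stayed below that. The failing arm's maximum therefore stays high, provided the triggering reading is counted. The exception is Investigator Discretion after 8 adjuvant weeks. The distortion comes mainly from BCL starts made for CEAE grade alone, and with equal rates of these no scenario reversed (0 of 144).

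A reader might also take 17 exams as this trial's typical case. It is a ceiling. Enrolment stopped at 40, follow-up was short, and exam data cease for continuing subjects.

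Other SAP analyses give protection. The primary endpoint includes the +0.3 criterion and keeps its window. Section 11.3 also plans time to BCL and time to +0.3 or CEAE Grade 3, both with censoring, where delayed BCL would show. The maximum is summarised without a test.

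Finally, stopping at BCL is defensible: Protocol 3.3 assesses the initial prophylaxis and the lens separately. Counting exams after BCL in the main definition would change the question.

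All of this stands and limits the size of the problem. None of it explains why the SAP omits a window that the protocol sets.

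**Conclusion.** The concern holds as a conflict between SAP and protocol with a usual direction of bias. As written, SAP 11.3 takes a maximum over exam counts that differ between arms and depend on the outcome. An arm that delays BCL tends to have its apparent benefit reduced: negligibly when CEAE-driven BCL starts are equally frequent (0.040 against 0.041 to 0.042 LogMAR), and from 0.036 to 0.023 at assumed rates of 10% against 5% per exam. Reversal requires clearly unequal CEAE-driven starts. It was common only at 20% or 30% against 5%, and rarer with truncated follow-up.

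Restoring the window reduces the bias but does not remove it, because the cut at BCL remains (34 of 360 scenarios still reversed, against 101). These sizes rest wholly on assumed effects, SDs, trigger rates and stopping. With about 13 subjects per arm, sampling error is larger than the average shifts. The change is still worth making: the conflict is plain and the correction is cheap. Short follow-up adds a reason, because under the open rule each subject's exam count also depends on when the subject enrolled.

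**What to change.** In SAP 5.3.2 and 11.3:

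- **Main definition.** Maximum change from baseline in binocular visual acuity (VA OU) with baseline correction and without BCL, over exams in the first 8 weeks after the first depatuxizumab mafodotin dose and prior to BCL. State that the no-lens reading at the visit where the lens is first placed counts.
- **Adjuvant phase.** Give a separate summary for the first 8 weeks of that phase, following Protocol 3.3. State whether Cycle 3 Day 1, which falls 2 × 28 = 56 days after Cycle 1 Day 1, is inside. Report how many subjects contribute, because those already on BCL are excluded.
- **Exam counts.** Report the number of contributing exams per arm.
- **Sensitivity summary.** Because the cut at BCL leaves some bias, repeat the 8-week maximum with available no-lens readings after BCL included, and count the missing readings.

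The cost is SAP wording and a few table rows, with no new data collection. The downsides are that fewer exams contribute (at most 3 scheduled in the first 8 weeks) and that no-lens readings after BCL will be incomplete: Operations Manual 3.5 omits them when the lens is not changed, and those gaps fall only in subjects who started BCL. That is why they belong in a sensitivity summary and not in the main definition.
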